#### *8.3.8.2 Definition of the AE Reporting Period*

The AE reporting period for safety surveillance begins when the patient is included into the study (ICF signature date) and continues through the end of the study's post-treatment follow-up period, defined as EoS (V9). AEs will be recorded on an ongoing basis in EDC. In case any AE occurs, the Investigator will follow up the patient within the AE reporting period until the event has resolved or the condition has stabilized. For SAEs, regardless of their relatedness to the IMP, the follow-up period might be extended, see Section 8.3.8.5.

All SAEs that the Investigator considers related to IMP occurring after the post-treatment follow-up period (V9-EoS, or Early Termination Visit) must be reported to POXEL as well as to Safety Provider (see contact details in Section 14. Annex 2. *Serious Adverse Event Contact Information*).

Only events that occur after the first intake of IMP of the double-blind treatment period (Randomization Visit (V1)) or if they were present prior to the first intake of IMP of the double-blind treatment period and increased in severity or relationship to IMP after the first intake of IMP of the double-blind treatment period will be considered as treatment-emergent AEs (TEAEs).

#### *8.3.8.3 Methods of Recording and Assessing Adverse Events*

Complete, accurate and consistent data on all AEs experienced for the duration of the reporting period (defined above in Section 8.3.8.2) will be reported on an ongoing basis in the appropriate section of the eCRF.

The following aspects must be recorded for each event in the source documents and in the eCRF for AE:

- A description of the AE in medical terms, not as reported by patients (AE verbatim)
- The date and time of onset (start date and time)
- The date and time of recovery (stop date and time)
- The severity grade (CTCAE Grade 1-5)
- Seriousness: yes or no
- The causal relationship to IMP as assessed by the Investigator; the decisive factor in the documentation is the temporal relation between the AE and the IMP. The following judgments of the causality to IMP or study procedures are to be used:

- Unrelated: IMP cannot be reasonably suspected, a reasonable explanation must be given
- Related: IMP can be reasonably suspected. AE could medically (pharmacologically/clinically) be attributed to the IMP
- Action taken on IMP (no change, temporary interruption, permanent discontinuation, not applicable)
- Other actions (none, corrective treatment, hospitalization or prolongation of hospitalization, other)
- The outcome and date of outcome according to the following definitions:
  - Recovered/resolved (AE disappeared)
  - Recovering/resolving (patient is recovering)
  - Not recovered/not resolved (AE remains without signs of improvement)
  - Recovered/resolved with sequelae
  - Fatal
  - Unknown (only applicable if patient has been lost to follow-up)

The following aspects must be recorded in the source documents and in the eCRF for SAE:

- All the above information listed for AEs
- Additional information:
  - A SAE medical term
  - A description of the SAE in medical terms, not as reported by patient; only the term(s) that fulfills the seriousness criteria should be listed (including sequence of events, symptoms, diagnosis, treatment and any other relevant information)
  - The seriousness criteria (as described in Section 8.3.8.1.3)

If a patient experienced the same AE several times during his/her participation in the study, then this AE must be documented and assessed as a new AE each time.

Each AE will be classified using the version of the Medical Dictionary for Regulatory Activities (MedDRA®) available at the start of the study.

#### *8.3.8.4 Sponsor immediate notification and Regulatory Reporting*

##### *8.3.8.4.1 Sponsor Immediate Notification*

The Investigator must report immediately (within 24 hours of the Investigator's awareness) to POXEL as well as to Safety Provider all SAE/AESI/Overdose/Pregnancy occurring from

the date of ICF signature to the End-of-study Visit (V9-EoS) or to the last study visit performed in case of premature discontinuation.

For SAE, AESI, overdose and pregnancy, the study site must complete the corresponding eCRF page with as much available information within 24 hours of knowledge of the event.

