**IMP should be discontinued and the patient should be withdrawn from the study in the event of any of the following:**

1. Occurrence of an AE or SAE which is clinically relevant and affects patient's safety (Common Terminology Criteria for Adverse Events (CTCAE) grade 3 or higher AE related to the drug **OR** CTCAE grade 4 or higher regardless of attribution to the study drug), if discontinuation of the IMP is considered necessary by the Investigator or POXEL Medical Representative
2. Occurrence of pregnancy
3. Important protocol deviation if discontinuation of IMP is considered necessary by the Investigator or POXEL Medical Representative/designee
4. Intake of non-permitted drug (as defined in Section 6.5 *Non-permitted Medicines*) if discontinuation of IMP is considered necessary by the Investigator or POXEL Medical Representative/designee
5. Requirement of an emergency unblinding (as described in Section 6.3.3.2 *Emergency Unblinding*)
6. Withdrawal of patient informed consent

7. Lost to follow-up
8. Sponsor decision (as defined in Section 5.9 *Discontinuation of the Study*)

In case of temporary interruption of the IMP, the decision to resume the IMP should be taken in agreement by the Investigator, POXEL Medical Representative and Medical Monitor.

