## 5.9 Discontinuation of the Study

The whole study may be discontinued by POXEL in the event of any of the following:

- New information leading to unfavorable risk-benefit ratio of IMP, e.g. due to:

- Occurrence of significant previously unknown adverse reactions or unexpectedly high severity or incidence of known adverse reactions, or
- Other unfavorable safety findings
- POXEL's decision that continuation of the study is unjustifiable for medical or ethical reasons
- Poor enrollment of patients making completion of the study within an acceptable time frame unlikely
- Discontinuation of development of the POXEL's IMP

The study will be paused if any of the following occurs:

- Three patients develop the same Grade 3 CTCAE classified as related to study drug
- Two patients develop the same Grade 4 CTCAE classified as related to study drug
- One patient develops a grade 5 CTCAE classified as related to study drug

In case the study is paused, the Sponsor will organize an *ad hoc* global safety board according to Sponsor's Standard Operating Procedures. This global safety board will assess the benefit/risk ratio in order to decide whether the study should be stopped or can be continued. This assessment/conclusion will be sent to Competent Authorities.

Competent Authorities and Institutional Review Boards/Ethics Committees (IRB/EC) will be informed about the discontinuation of the study in accordance with applicable regulations.

The study may be terminated or suspended upon request of Competent Authorities.

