#### 8.3.6 *Laboratory Assessments*

All laboratory measurements will be performed by a central laboratory using samples collected at the visits shown in the Visit Schedule Chart in *Table 1*. However, if judged necessary for the safety of the patients, the Investigator or POXEL may request unscheduled central laboratory assessments.

Blood samples will be collected, handled and stored according to the instructions described in the central laboratory manual.

A list of normal reference ranges will be provided by the central laboratory to POXEL and the Investigators before the study start. Any change in the normal reference ranges during the study will be forwarded by the central laboratory to POXEL and the Investigators, who will have to keep it in the Trial Master File (TMF) and respectively, in the Investigator Site File (ISF).

Central laboratory reports must be reviewed by the Investigator as soon as received. Each parameter must be assessed by the Investigator and the clinical significance of the abnormal

parameters must be documented. To confirm the review, the Investigator will have to sign and date the report and keep it in the patient file.

Any new clinically significant findings or worsening of laboratory abnormalities previously recorded as Medical History will be reported as AEs, and followed up and/or treated locally until the AE has resolved or the condition has stabilized. The CTCAE criteria, version 5.0, will be used to determine severity.

The following panel will be evaluated.

*8.3.6.1 Standard Safety Laboratory Panel (Blood and Urine)*

Hematology	Biochemistry	Urinalysis
Erythrocytes	Blood Urea Nitrogen	pH
Hemoglobin	Creatinine	Specific gravity
Hematocrit	Sodium	Protein
Red Blood Cell Morphology	Potassium	Glucose
Mean corpuscular volume	Chloride	Ketones
Mean corpuscular hemoglobin	Bicarbonate	Nitrites
Mean corpuscular hemoglobin concentration	Calcium	Urobilinogen
Leucocytes	Inorganic phosphate	Blood
Differential blood count (lymphocytes, monocytes, eosinophils, basophils, neutrophils/ absolute values and percentages should be given)	Total protein	Leucocytes
Thrombocytes	Albumin	If the dipstick result is abnormal: microscopic examination of the sediment for blood cells, cylinders, etc.
	Uric acid	
	Creatine phosphokinase	
	AST	
	ALT	
	GGT	
	TBL	
	ALP	
	hsCRP	
	TSH (during Screening Period only)	
Coagulation		
	aPTT	
	PT	
	INR	

*8.3.6.2 Viral Infection Screen Panel*

Hepatitis screening	HIV screening
HBsAg	Anti-HIV 1 and 2

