#### 8.3.8.1 Adverse Event Definitions

##### 8.3.8.1.1 Adverse Event (AE)

An AE is any untoward medical occurrence in a patient or clinical investigation patient administered a pharmaceutical product, which does not necessarily have a causal relationship with this treatment. An AE can therefore be any unfavorable and unintended sign (including an abnormal laboratory finding), symptom, or disease temporally associated with the use of a medicinal, whether or not considered related to the medicinal product.

The official definition also extends to AEs occurring under placebo or in a reference group receiving drug or non-drug therapy. Because of regulatory requirements, events occurring during drug-free and pre- and post-treatment periods should also be designated as AEs.

Therefore, safety surveillance applies to the time when the patient is included into the study (date of ICF signature) until the End-of-Study Visit (V9-EoS) performed two weeks after the End-of-Treatment Visit (V8-EoT).

In cases of surgical or diagnostic procedures, the condition/illness leading to such a procedure is considered as the AE rather than the procedure itself.

Adverse events will be assessed according to the Common Terminology Criteria for Adverse Events (CTCAE) version 5.0.

The Investigator is required to grade the severity/intensity of each AE according to CTCAE:

- CTCAE Grade 1: Mild; asymptomatic or mild symptoms; clinical or diagnostic observations only; intervention not indicated
- CTCAE Grade 2: Moderate; minimal, local or noninvasive intervention indicated; limiting age-appropriate instrumental activities of daily living (ADL)
- CTCAE Grade 3: Severe or medically significant but not immediately life-threatening; hospitalization or prolongation of hospitalization indicated; disabling; limiting self care ADL
- CTCAE Grade 4 (Life threatening): life-threatening consequences; urgent intervention indicated

- CTCAE Grade 5 (Death): death related to AE

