#### 8.3.8.1.4 Adverse Event of Special Interest (AESI)

An AE of Special Interest (AESI, serious or non-serious) is one of scientific and/or medical concern specific to the Sponsor's product or program, for which ongoing monitoring and rapid communication by the investigator to the Sponsor can be appropriate. Such an event might warrant further investigation in order to characterize and understand it. Depending on the nature of the event, rapid communication by the trial Sponsor to other parties (e.g., regulators) might also be warranted.

Even if non-serious, AESI are managed with the same process than SAE:

- notification to the Sponsor within 24h following investigator awareness
- case to be created and processed in the safety database (including narrative writing) by Safety Provider.

In this study, the following AEs are considered as AESI:

- Heart failure. In case of any event of heart failure, whatever the cause, patients should be referred to a cardiology specialist.
- Pitting edema. In case of occurrence of pitting edema with presence of other suspected signs and/or symptoms of heart failure, patients should be referred to a cardiology specialist.
- Bladder cancer
- Bone fracture
- Drug-induced liver injury (DILI)

**Below are specific recommendations for the management of elevated liver transaminases and/ or total bilirubin to detect and monitor a possible DILI, following FDA guidelines:**

- **For patients with normal liver transaminases and total bilirubin at baseline (Randomization Visit (V1)):**

If patients with normal baseline (Randomization Visit (V1)) liver indices develop new elevations of AST or ALT  $>3 \times$  ULN or TBL  $>2 \times$  ULN values during the study, repeat testing should be performed within 48 to 72 hours. Investigators should also ask the patient if he/she has symptoms.

If there are persistent elevations (ALT or AST  $>3 \times$  ULN or TBL  $>2 \times$  ULN) upon repeat testing, then close observation (as described below) should be implemented and discontinuation of drug should be considered.

Drug should be discontinued, and the patient followed until resolution of symptoms or signs in the following situations:

- ALT or AST  $>8 \times$  ULN
- ALT or AST  $>5 \times$  ULN for more than 2 weeks.

- ALT or AST  $>3 \times$  ULN and (TBL  $>2 \times$  ULN or INR  $>1.5$ , except for patients on anticoagulant treatment)

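### Related, non-serious Grade 3 events count toward the study pause in section 5.9, but a small group of them falls outside the 24-hour sponsor notification list

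*Protocol*

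**What the plan says.** **Pause rule.** Protocol 5.9 pauses the whole study on any of three counts of related events by CTCAE grade. The lowest-grade count is "Three patients develop the same Grade 3 CTCAE classified as related to study drug"; the others are two patients with the same Grade 4 event and one patient with a Grade 5 event. Seriousness is not a condition. A safety board is convened ad hoc once the study is paused.

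**24-hour duty.** Protocol 8.3.8.4.1 requires notice to the sponsor and the safety provider within 24 hours of the investigator's awareness for four categories, and adds: "For SAE, AESI, overdose and pregnancy, the study site must complete the corresponding eCRF page with as much available information within 24 hours". Section 11.1 repeats the same four categories. CTCAE grade does not appear in either list.

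**Other fast routes.** Section 8.3.8.1.4 states: "Even if non-serious, AESI are managed with the same process than SAE". Section 5.8.2 requires immediate notice of every withdrawal to the Medical Monitor and the sponsor's medical representative.

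**Everything else.** Section 8.3.8.2 says "AEs will be recorded on an ongoing basis in EDC", and 8.3.8.3 says AE data "will be reported on an ongoing basis in the appropriate section of the eCRF". Neither gives a time. Section 11.1 asks for eCRF completion as soon as possible after each visit, with 5 business days as the outer limit.

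**The concern.** The pause rule runs on grade and causality. The notification rule runs on seriousness and a short list of special cases. The protocol itself warns, in 8.3.8.1.3, that severe and serious are not the same thing. An event can therefore count toward a mandatory pause without any duty on the site to tell the sponsor quickly.

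This is a patient-safety matter, because a pause across sites can start only when the sponsor knows that the count has been reached. In a multi-center trial each site sees its own cases only. The investigator can and must act at once for the affected patient if continued dosing is thought harmful (5.8.1), but that does nothing for patients elsewhere.

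**Working it through.** The plan gives no figure to reproduce. The check is a cross-reading, followed by one small piece of arithmetic.

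**Step 1. Which triggering events already reach the sponsor quickly?**

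| Event counting toward 5.9 | Route | Time stated |
|---|---|---|
| Grade 5, and nearly all Grade 4 | Death or life-threatening, hence SAE (8.3.8.1.1, 8.3.8.1.3) | 24 hours |
| Grade 3 meeting an SAE criterion | SAE | 24 hours |
| Heart failure, pitting edema, bladder cancer, bone fracture, confirmed DILI | AESI, serious or not (8.3.8.1.4) | 24 hours |
| Any event leading to withdrawal | Withdrawal notice (5.8.2) | Immediate |
| Related Grade 3, non-serious, non-AESI, drug interrupted | Sponsor must agree before drug is resumed (5.8.1) | None for first notice |
| Related Grade 3, non-serious, non-AESI, dosing unchanged | Ongoing EDC entry (8.3.8.2, 8.3.8.3); eCRF rule (11.1) | 5 business days after a visit; none between visits |

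The last two rows are the gap, and the last row is most of it.

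**Step 2. Does withdrawal empty those rows?** No. Section 5.8.1, item 1, stops drug for a related Grade 3 event only "if discontinuation of the IMP is considered necessary by the Investigator or POXEL Medical Representative". That is discretionary, and it sets no time for telling the sponsor.

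**Step 3. Can the last rows contain real events?** Yes, though few.
- The protocol's Grade 3 definition is "Severe or medically significant but not immediately life-threatening; hospitalization or prolongation of hospitalization indicated; disabling; limiting self care ADL". Parts of it overlap the SAE criteria (hospitalization, disability). A severe event, or one limiting self-care, need not meet any of them.
- Section 8.3.6 provides a second source: "Any new clinically significant findings or worsening of laboratory abnormalities previously recorded as Medical History will be reported as AEs", graded by CTCAE. The text on abnormal findings in 8.3.8.1.3 narrows this. A laboratory abnormality becomes an AE only if it comes with signs or symptoms, leads to stopping drug, or is judged medically important. The second of these normally leads to withdrawal, and the third sits close to an SAE criterion. Mainly symptomatic laboratory findings remain.

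**Step 4. How late could the sponsor learn of such an event?**
- Inputs: 24 hours from awareness (8.3.8.4.1); 5 business days from the visit (11.1).
- Assumptions: a weekday visit, no public holiday, and the event recognized, graded and judged related at that visit, so that both clocks start on the same day.
- Five business days from any weekday span one weekend: 5 + 2 = 7 calendar days.
- Excess over the 24-hour standard: 7 − 1 = 6 calendar days.

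For an event learned of between visits, including a laboratory report arriving after the visit, the eCRF limit counts from the visit and not from awareness. Only the untimed instruction to enter data on an ongoing basis applies, so no bound can be calculated.

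**The case against.** The strongest reply is that nothing here is inconsistent. Section 5.9 sets no time for detecting the third event, and 8.3.8.1.3 names seriousness, not severity, as the guide to regulatory reporting. The first half stands: a reader might infer that the two sections contradict each other, and they do not. The second half does not answer the point. That sentence concerns reports to authorities, whereas the question here is how the sponsor's own pause rule receives its data.

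Second, the group is narrow. The laboratory filter, the overlap between Grade 3 and the SAE criteria, and the agreement needed before interrupted drug is resumed all shrink it. This stands, and the group described here allows for all three.

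Third, 6 days is an outer limit. Sites are told to complete the eCRF as soon as possible, so the usual delay is probably shorter. This also stands.

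Fourth, section 11.1 refers to an Adverse Event Reporting Plan and to eCRF completion guidelines, neither of which was available. Either may already ask sites for faster notice of these events. That applies to timing as much as to who counts events across sites, and it limits confidence in the practical effect.

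Fifth, adding a category to the 24-hour list is not free. AESIs receive a safety-database case with a narrative, and all four listed categories are reconciled with the clinical database. This stands and shapes the fix.

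**Conclusion.** The gap is real but small. Followed exactly as written, the protocol allows a mandatory pause to be triggered up to about 6 calendar days later than under a 24-hour rule when the deciding event is found at a visit. It sets no limit when that event is learned of between visits. The 6 days require that the event completing the count belongs to the residual group and that the site uses the full allowance. SAEs, AESIs and events leading to withdrawal are unaffected, and no data are lost: grade, seriousness and causality are all recorded.

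A reader might convert the 6 days into six extra daily doses for every patient on treatment. The documents do not support that. Section 5.9 says the study is paused without saying whether dosing, enrollment or both stop. Nor can the delay be turned into a risk, because the documents give no basis for estimating how often such events occur.

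This is a cheap improvement of low priority, not a defect in the pause rule itself.

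**What to change.** In 8.3.8.4.1 and 11.1, require sites to notify the sponsor's medical representative and the Medical Monitor, within 24 hours of awareness, of any AE of CTCAE Grade 3 or higher that is classified as related to the investigational product. Send this through an alert on the eCRF AE page, built on the grade and causality fields already collected. Extend the manual back-up procedure so that email serves when EDC is unavailable.

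State that non-serious, non-AESI events notified in this way do not enter full SAE case processing. Leave the 5.9 thresholds and the seriousness-based regulatory reporting unchanged. Before amending, check whether the Adverse Event Reporting Plan or the eCRF completion guidelines already contain part of this.

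The cost is a short protocol amendment, the eCRF alert, a modest number of extra site notifications, and some added medical review and reconciliation.

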### **Manual Back-Up Reporting Procedures**

This study is utilizing an Electronic Data Capture (EDC) system for data entry. In the event that the EDC system is unavailable for electronic reporting, the manual back-up reporting procedures below should be followed:

- Complete a SAE or Pregnancy/Overdose Form
- Email the form to POXEL as well as to Safety Provider (fax can be used as second option), contact details in Section 14. Annex 2. *Serious Averse Event Contact Information*.

When the EDC system becomes available, the EDC system should be updated with all previously reported information.

#### **8.3.8.4.2 Reporting to Regulatory Authorities (Expedited Reporting), Investigators and Independent Ethics Committees/Institutional Review Boards**

SUSARs and other safety information requiring expedited reporting will be reported to Investigators, Ethics Committees as well as Competent Authorities in agreement with applicable guidelines and US regulations.

In accordance with ICH GCP guidelines, POXEL/ will inform the Investigator of “findings that could adversely affect the safety of patients, impact the conduct of the study or alter the IRB/EC’s approval/favorable opinion to continue the study.” In particular, and in line with respective US regulations, POXEL will inform the Investigator of AEs that are both serious and unexpected and are considered to be related to the administered product (SUSARs). The Investigator should place copies of these safety reports in the ISF. National regulations with regard to safety report notifications to Investigators will be considered.

